8.4.3 Adverse Events of Special Interest

Events defined below are considered AESI for this trial and should be reported following SAE reporting procedures (Section 12.3).

[figure not shown]
8.4.3.1 Drug Induced PR Prolongation

[figure not shown]
Drug-induced PR prolongation with Mobitz type 1 second degree AV block may be a risk associated with ASN51. TEAEs with the following Medical Dictionary for Regulatory Activities (MedDRA) Preferred Terms (PTs) will be considered an AESI for this trial:

[figure not shown]
 AV block first degree, AV block second degree Mobitz type I, AV block second degree Mobitz type II, and AV block third degree.

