If a clinically significant finding is identified (including changes from baseline in QTcF) after enrollment, the Investigator or qualified designee will determine if the participant may continue in the trial or if a change in participant management is required. Review of ECGs must be documented upon collection and any new clinically significant ECG finding should be reported as an AE. Central review of ECGs will also be performed (see Section 8.3.3.1).

Should the following events occur in an individual participant during the trial, the Investigator, in consultation with the Sponsor's Medical Monitor, will decide if study intervention should be interrupted or permanently discontinued:

- If a participant has median PR interval of 200 ms to 220 ms AND a change from baseline in PR interval of > 10% (triplicate measurements)
- If a participant has median PR interval > 220 ms (triplicate measurements).

Systemic Hypersensitivity Reactions

If the Investigator, after consultation with the Sponsor-designated Medical Monitor, determines that a systemic hypersensitivity reaction has occurred related to IMP administration, the participant should be discontinued.

Excluded Therapeutic Agent

If the participant requires treatment with an excluded therapeutic agent and temporary discontinuation cannot be met, IMP should be discontinued.

If a participant discontinues from the trial prematurely, reasonable efforts should be made to perform the Early Termination (ET) visit procedures as soon as possible, and schedule Follow-up Visit procedures 4 weeks after the last dose of ASN51.

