9.2 Analysis Supporting Primary Objective - Safety

All safety analyses will be conducted in the Safety Analysis Set.

Adverse Events

Safety will be evaluated by examining incidence, type, causality, and severity of TEAEs, including SAEs and discontinuation due to TEAE.

Adverse events will be classified according to the latest available MedDRA version, to the SOC and PT levels. Treatment-emergent AEs (hereafter referred to as AEs) are defined as those with onset after the first dose of randomized treatment intervention at Day 1 or, if occurring prior to administration of the first dose at Day 1, worsened after administration of that first dose.

The AE listings will indicate whether the event led to temporary interruption of or permanent withdrawal of study treatment. An overall summary will be presented which gives the number and percentage of participants within each dose group in the safety population that experienced any AE, experienced any treatment-related AE, temporarily interrupted or permanently discontinued treatment due to an AE, experienced an SAE, and that died.

Incidence of Adverse Events

The number and percentage of participants experiencing one or more AE within a MedDRA SOC and PT without regard to intensity, relationship, or seriousness will be tabulated.

Tables will also be prepared to display events by SOC, PT, and maximum intensity or closest relationship to treatment.

A glossary listing that shows the verbatim terms assigned to each SOC and PT will be provided.

Severity of Adverse Events

A summary of AEs by severity will be presented in a table by incidence of occurrence. The severity that will be presented represents the most extreme severity captured on the eCRF page. The severity will be assessed by the Investigator as "Mild," "Moderate," or "Severe." If a participant reports multiple occurrences of the same AE (at the PT within the SOC level and at the SOC level), only the most severe will be presented.

Relationship of Adverse Events to Study Treatment

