12.3 Reporting of Serious Adverse Events

SAEs and AESIs must be reported to the Sponsor (or designee) within 24 hours of the knowledge of the occurrence.

An SAE report will be completed as thoroughly as possible including all available details about the event and the signature of the Investigator. The SAE form will be updated when additional information is received.

A death occurring during the trial must be reported to Sponsor or its designee within 24 hours of knowledge of the death whether or not it is considered treatment related.

The Investigator also must notify the IRB/IEC of the occurrence of the SAE, in writing, as soon as is practicable and in accordance with IRB/IEC requirements and local law. A copy of this notification must be provided to the Sponsor or its designee.

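### The AESI headed Drug Induced PR Prolongation is assigned through AV-block terms in the visible list, so a non-serious event coded as PR prolongation is not an AESI and has no 24-hour reporting clock

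*Combined protocol and SAP*

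**What the plan says.** Section 8.4.3.1 is headed Drug Induced PR Prolongation and opens with the risk: "Drug-induced PR prolongation with Mobitz type 1 second degree AV block may be a risk associated with ASN51". It then gives the rule for assigning status: "TEAEs with the following Medical Dictionary for Regulatory Activities (MedDRA) Preferred Terms (PTs) will be considered an AESI for this trial". The visible terms are "AV block first degree, AV block second degree Mobitz type I, AV block second degree Mobitz type II, and AV block third degree".

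Section 8.4.3 sends AESIs down the SAE reporting route, and Section 12.3 sets the clock: "SAEs and AESIs must be reported to the Sponsor (or designee) within 24 hours of the knowledge of the occurrence".

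PR findings are also handled elsewhere:

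- Section 7.1.1 (ECG) says that "any new clinically significant ECG finding should be reported as an AE". It lists two PR conditions on triplicate ECGs: a median of 200 to 220 ms with a change from baseline above 10%, and a median above 220 ms. At either one the Investigator, consulting the Sponsor's Medical Monitor, decides whether to interrupt or stop study intervention.
- Section 5.4.2 excludes a median PR above 200 ms at Screening.
- Section 8.3.3.1 has ECGs read centrally, with PR among the parameters, and leaves clinical significance to the Investigator.
- Section 9.6.4 summarises PR as an ECG parameter.

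**The concern.** An AESI definition marks events that the sponsor wants to see quickly and count consistently. Here the heading and the risk sentence describe a lengthened PR interval, while the rule recognises only coded AV-block terms in the visible text. The most direct description of the named risk, PR prolongation, matches none of them.

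Two consequences follow. First, whether a non-serious ECG finding becomes an AESI turns on the Preferred Term it is coded to, and the visible text does not say which term a long PR interval should receive. Two sites with equivalent tracings could produce one AESI and one ordinary AE. Second, the PR conditions that Section 7.1.1 treats as serious enough for a decision on study intervention have no bearing on AESI status. Safety is the primary objective, so an inconsistent AESI set for a cardiac conduction risk is worth correcting.

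**Working it through.** No arithmetic applies. The check sets the definition, the reporting route and the other PR provisions side by side.

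**Step 1: the name against the list.** The heading and risk sentence in 8.4.3.1 name PR prolongation. The visible list has four terms, of which four are AV block and none is a PR-prolongation term. The definition contains no PR-interval threshold and no reference to 7.1.1.

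**Step 2: what AESI status adds.** Under 8.4.3 and 12.3 it brings the SAE reporting route and the 24-hour clock. An ordinary non-serious AE has neither.

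**Step 3: follow the possible cases through the text.**

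| Event | AESI? | 24-hour clock? |
|---|---|---|
| Serious, coded to a PR-prolongation term | No | Yes, as an SAE |
| Non-serious, coded as first degree AV block | Yes | Yes, as an AESI |
| Non-serious, coded to a PR-prolongation term | No | No |
| As the row above, and meeting a 7.1.1 PR condition | No | No; Medical Monitor consulted, no time limit stated |

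The second and third rows can describe the same tracing. Only the coded term differs.

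**Step 4: do the other provisions close the gap?**

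- The AE requirement in 7.1.1 gets a clinically significant finding recorded, but sets no 24-hour limit.
- The two PR conditions bring in the Medical Monitor, but again without a time limit and without making the event an AESI.
- Section 9.6.4 serves the analysis of PR values and does nothing for prompt reporting.
- The Screening exclusion means that an on-study median above 200 ms is new since Screening. Such values are therefore the kind of change the AESI is named for.

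None of these provisions supplies AESI status or the clock.

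**Step 5: can the size be computed?** No. The documents give no PR distribution, no expected shift, and no proportion of PR findings that would be coded to one term or another. Any participant count would rest wholly on outside assumptions.

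**The case against.** The strongest reply is that little is lost in practice.

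- First degree AV block is on the list, which is consistent with an intention to capture simple PR lengthening. If coders place every long PR interval there, the gap closes. This has force, but the visible text states no such coding rule, and 9.2.1 says only that the investigators' original terms are coded in MedDRA.
- The argument assumes that the dictionary version in use has a separate PR-prolongation Preferred Term. The documents do not show this. It stands as an assumption, and the fix allows for either case.
- In the public text a figure marker sits between the lead-in sentence and the list. A lost list item cannot be excluded, so the point is confined to the visible terms.

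A reader might also infer more than the documents support:

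- *That PR prolongation escapes 24-hour reporting altogether.* It does not. A serious event goes out within 24 hours as an SAE, and an event coded to a listed term goes out as an AESI.
- *That the sponsor would not learn of the finding.* At both 7.1.1 PR conditions the Medical Monitor is consulted, and Section 10.2.2 places that role on the Safety Review Committee. What is missing is the explicit clock and the AESI label.
- *That the safety evidence or a dose comparison is compromised.* PR is analysed from ECG data whatever the AE coding (9.6.4), all TEAEs are tabulated by System Organ Class and Preferred Term (9.2), and the visible text plans no between-dose AESI comparison.
- *That the absence of an AESI line from the overall AE summary in 9.2 is itself a defect.* Section 9 says the analyses will be expanded in the SAP, so this is a reporting detail that can be settled there.

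**Conclusion.** The point holds in a limited form. On the visible text the AESI rule misses part of the risk it is named for. A non-serious event coded as PR prolongation is not an AESI and has no 24-hour clock, even when it meets a 7.1.1 PR condition, while the same finding coded as first degree AV block has both. The defect is one of ascertainment and prompt reporting.

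Its extent cannot be put into numbers. It depends on how many PR findings are recorded as AEs and how they are coded, and the documents give neither. The conclusion rests on two assumptions: that the visible list is complete, and that a long PR interval can be coded to a term other than the four listed. If the full text contains a PR-prolongation term, only the missing link to 7.1.1 remains. The correction is specific and cheap, and should be made.

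**What to change.** Reconcile the heading of 8.4.3.1, its term list and the PR conditions in 7.1.1:

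1. Add to the list the PR-prolongation Preferred Term of the MedDRA version in use. Alternatively, state in 8.4.3.1 and the coding conventions that such findings are coded to one of the listed terms.
2. State that an AESI is also identified from central ECG data when either PR condition already in 7.1.1 is met, so that ascertainment does not rest on AE coding alone.

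This leaves the 7.1.1 conditions and the decisions taken under them as they are; only AESI identification and reporting change. The cost is a sentence or two in 8.4.3.1, a programmed flag on the central ECG data, and a few more expedited reports.

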8.4.3.2 Drug Induced Liver Injury

The potential for drug-induced liver injury will be monitored using assessments of liver function via serum chemistry at regular intervals. If the AST or ALT is $> 1 \times ULN$ but $< 2 \times ULN$, the Investigator should determine whether more frequent testing is warranted. If the AST or ALT is $\geq 2 \times ULN$ with or without bilirubin or alkaline phosphatase elevation, but do not meet the

8.10 Immunogenicity

Not applicable.

8.11 Medical Resource Utilization and Health Economics

Not applicable.

9 STATISTICAL CONSIDERATIONS

A general description of the statistical methods planned to analyze the safety and preliminary efficacy of the IMP is outlined below. The analyses specified in this protocol will be expanded in the Statistical Analysis Plan (SAP) to include a detailed description of the analyses. The SAP will be finalized and approved prior to database lock.

Trial data will be reported using summary tables, figures, and data listings. Descriptive statistics will be used to summarize the data. For continuous variables, the mean, standard deviation, median, minimum, and maximum will be provided. For discrete data, incidence and percentages will be provided. Statistical tests will be 1-sided at the alpha level of 0.10, unless stated otherwise. P-values will be used descriptively and will have no inferential value. All p-values will be reported to the 3rd decimal place. Summary tables will include the data from the ASN51 groups combined, i.e., Placebo and ASN51 for the DB and LTE periods, respectively.

Baseline for all clinical laboratory evaluations, vital signs measurements, and 12-lead ECGs will be defined as the last evaluation before IMP administration. The timing of each protocol-specified assessment is provided in the Schedules of Activities (Section 1.3).

Two sets of analyses will be conducted. The first set of analyses will be conducted after all participants have had the opportunity to complete the Week 24 assessment or have discontinued the study (primary analysis Sections 9.1 through 9.7). The second set of analyses will be conducted when all participants have had the opportunity to complete the LTE or discontinued the study (Section 9.8).

For endpoints collected only once post-baseline, changes from baseline will be analyzed using an analysis of covariance (ANCOVA) model that includes the categorical effects of APOE4 status, use of AD medication, treatment group, and the continuous covariate of the baseline value of the variable being analyzed. The one-sided p-value (t-test on least squares means at Week 24) and two-sided 80%, and 90% confidence limits will be tabulated. The model will also include the randomization stratification factors (i.e., APOE4 status and use of AD medication).

For endpoints collected multiple times post-baseline, changes from baseline will be analyzed using a restricted likelihood-based mixed effects model for repeated measures (MMRM). Change from baseline will be fit as the dependent variable. Independent variables included in the analysis model will be the categorical fixed effects of APOE4 status, use of AD medication, treatment group, and the treatment by Visit interaction, along with the continuous covariates of the baseline value of the variable being analyzed and its interaction with Visit. The model will also include the randomization stratification factors (i.e., APOE4 status and use of AD medication). Within participant errors will be modeled using an unstructured covariance matrix. If this analysis fails to converse, heterogeneous Toeplitz, heterogeneous auto-regressive, and heterogeneous compound symmetric structures will be tested in the listed order. The first structure to yield

convergence will be considered the primary analysis. The one-sided p-value (t-test on least squares means at Week 24) and two-sided 80%, and 90% confidence limits will be tabulated.

Analysis of PK parameters may be described and summarized in a separate document outside the context of the SAP.

Data analysis will comply with principles set forth in the International Conference on Harmonisation (ICH) E9 Guideline and ICH E9(R1) Guideline.

9.1 Analysis Sets

The number of participants randomized who complete each trial Period and who discontinue the trial will be summarized. Reasons for discontinuation will be summarized. The following analysis sets will be employed:

9.1.1 Modified Intent-to-Treat

The modified Intent-to-Treat (mITT) Analysis Set will include all participants who received at least one dose of IMP. Participants will be included in the assigned dose cohort/arm, regardless of the actual treatment received.

9.1.2 Safety Analysis Set

The Safety Analysis Set consists of all participants who receive at least one dose of IMP. This analysis set will be used for the analyses of all safety endpoints. Participants will be included based on the actual dose level received.

9.1.3 Per Protocol Set

The Per Protocol Analysis Set will consist of participants who did not have major protocol violations with regard to entry criteria, adherence to IMP dosing, disallowed concomitant medications, and completion of study visits and procedures. A detailed list of participants with major protocol violations will be determined and documented prior to unblinding.

9.1.4 Pharmacokinetic Analysis Set

The PK Analysis Set will consist of all participants from whom plasma or CSF samples for the analysis of ASN51 were obtained and who did not have major protocol deviations that would confound interpretation of PK analysis.

9.2 Analysis Supporting Primary Objective - Safety

All safety analyses will be conducted in the Safety Analysis Set.

Adverse Events

Safety will be evaluated by examining incidence, type, causality, and severity of TEAEs, including SAEs and discontinuation due to TEAE.

Adverse events will be classified according to the latest available MedDRA version, to the SOC and PT levels. Treatment-emergent AEs (hereafter referred to as AEs) are defined as those with onset after the first dose of randomized treatment intervention at Day 1 or, if occurring prior to administration of the first dose at Day 1, worsened after administration of that first dose.

The AE listings will indicate whether the event led to temporary interruption of or permanent withdrawal of study treatment. An overall summary will be presented which gives the number and percentage of participants within each dose group in the safety population that experienced any AE, experienced any treatment-related AE, temporarily interrupted or permanently discontinued treatment due to an AE, experienced an SAE, and that died.

Incidence of Adverse Events

The number and percentage of participants experiencing one or more AE within a MedDRA SOC and PT without regard to intensity, relationship, or seriousness will be tabulated.

Tables will also be prepared to display events by SOC, PT, and maximum intensity or closest relationship to treatment.

A glossary listing that shows the verbatim terms assigned to each SOC and PT will be provided.

Severity of Adverse Events

A summary of AEs by severity will be presented in a table by incidence of occurrence. The severity that will be presented represents the most extreme severity captured on the eCRF page. The severity will be assessed by the Investigator as "Mild," "Moderate," or "Severe." If a participant reports multiple occurrences of the same AE (at the PT within the SOC level and at the SOC level), only the most severe will be presented.

Relationship of Adverse Events to Study Treatment

A summary of AEs by relationship to study treatment will be presented in a table by incidence of occurrence. The relationships will be collected based on the Investigator's determination of likelihood that study treatment could have caused the event. The possible relationships are "Unrelated", "Unlikely", "Possibly," "Probably," and "Definitely." For the summary of relationships, the categories of "Possibly," "Probably," and "Definitely" will be combined to form a single category of "Related." In the AE relationship table, if a participant reports multiple occurrences of the same AE (at the PT within SOC level and at the SOC level), only the occurrence with the greatest causal relationship will be presented. AEs that are missing relationship data will be presented in the summary table as "Related" but will be presented in the data listing with a missing relationship.

Adverse Events Leading to Treatment Discontinuation

All AEs for which the action "Study treatment discontinued" is recorded will be tabulated.

Serious Adverse Events

The data for SAEs will be presented in a listing. If a sufficient number of SAEs are reported, the severity and relationship tables can be subsetted on the SAE subpopulation.

Death

The data for participant deaths, if any, will be presented in a listing.

Changes from baseline in clinical laboratory test values, physical and neurologic examination results, vital signs measurements, and 12-lead ECGs will be listed and/or summarized through the end of trial.

9.2.1 Adverse Events

The original terms used in the eCRFs by investigators to identify AEs will be coded using the latest available MedDRA version. The number and percentage of participants with TEAEs will be summarized by treatment group. Summaries will be developed for those participants who discontinued treatment due to an AE or who experienced a life-threatening or treatment-emergent SAE.

9.2.2 Statistical Model, Hypothesis and Method of Analysis

Given the exploratory nature of the study, no formal statistical hypothesis will be performed. Nominal p-values for safety endpoints will be reported for descriptive purposes. Analyses will be based on Fisher's Exact Test

9.2.3 Handling of Missing Data

Adverse events with missing or partial onset date will be treated as TEAEs unless the partial onset date or end date of the event is complete enough to indicate that the event started or resolved prior to the first administration of the study intervention, in which case it will be documented in medical history. If AE grade or relationship is missing in analyses of grade and causality, the missing grade will be set to severe, and relationship will be set to related for tabulation purposes. Procedures for imputation of missing or partial AE start and end dates will be specified in the SAP.

Handling of missing data for secondary efficacy endpoints is described in Section 9.3.

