2.2.2 Risk Summary

2.2.2.1 Intervention Risks and Mitigation

2.2.3 Overall Benefit: Risk Conclusion

3 OBJECTIVES AND ENDPOINTS

Objectives	Endpoints							
Primary								
To evaluate the safety and tolerability of daily doses of ASN51 as compared with placebo	Incidence and severity of AEs Changes from baseline in laboratory safety assessments (including clinical chemistry, hematology, urinalysis, and serum hormone markers), Changes from baseline in vital signs, 12-lead electrocardiograms, and physical (including neurological) examinations Changes from baseline in C-SSRS							
Key Secondary								
To evaluate the effect of daily doses of ASN51 as compared with placebo on the pathophysiology of early AD To evaluate the effect of ASN51 versus placebo in change from Baseline to Week 24 on the pathophysiology of early AD	Change from baseline through Week 24 in CSF pTau217 Change from baseline through Week 24 in CSF total tau protein Change from baseline through Week 24 in plasma pTau217							
Other Secondary								
To evaluate the effect of daily doses of ASN51 as compared with placebo on tau pathology in early AD	Change from baseline through Week 24 in MK-6240 tau PET signal							
To evaluate the pharmacokinetics of ASN51 in early AD	Trough (C _{min}) at steady state and maximum (C _{max}) concentration of ASN51 in plasma at steady state through Week 24							
Tertiary/Exploratory								
To evaluate the effect of daily doses of ASN51 as compared with placebo on the pathophysiology of early AD To evaluate the effect of ASN51 versus placebo in change from Baseline to Week 24 on biomarkers of early AD	 Change from baseline through Week 24 in biomarkers, including but not limited to: Plasma Phosphorylated tau 181, GFAP, Aβ42/40, NFL CSF Phosphorylated tau 181, microtubule binding region tau 243, GFAP, Aβ42/40, NFL, neurogranin 							

ct of daily doses of with placebo on in early AD Change from baseline through Week 24 in: CDR-SB score ADAS-Cog13 score MMSE score ADCOMS score						
com Baseline to cructure Change from baseline through Week 24 in volumetric brain MRI parameters (e.g., whole brain volume, lateral ventricular volume, and cortical thickness measures of certain brain regions)						
Extension Period						
-term safety and 1 in early AD The incidence and severity of AEs over the DB placebo-controlled and LTE periods of the study						

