8.4.1 Time Period and Frequency for Collecting Adverse Event Information

All AEs, SAEs, AESI, and partner pregnancies occurring during the protocol-specified timeframes (Table 7) will be assessed and reported per guidelines provided in Section 12.

Table 7 Adverse Event Reporting Periods

Event Type	Reporting Period	Additional Requirements
AE/SAE during Screening Period	Date of participant informed consent through start of Day 1 Visit (prior to first dose of IMP)	Report as AE/SAE only if related to trial-specified procedure (medical history otherwise)
Treatment-emergent AE/SAE	First dose of IMP through 4 weeks post final dose of IMP	Report SAEs outside of reporting period if assessed as related to IMP
AESI	First dose of IMP through 4 weeks post final dose of IMP	Report AESI outside of reporting period if assessed as related to IMP
Pregnancy of partner	Date of participant informed consent through 4 weeks post final dose of IMP	Obtain consent to follow partner pregnancy

AE = adverse event; AESI = adverse event of special interest; IMP = investigational medicinal product; SAE = serious adverse event.

Clinically significant changes from baseline in any safety or clinical laboratory parameter will be recorded as AEs or SAEs, if deemed appropriate by the Investigator.

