12.1.2 Adverse Event

An AE is any untoward medical occurrence associated with the use of a drug in humans, whether or not considered drug related. The term "adverse event" could include any of the following events that develop or increase in severity during the course of the trial. Examples include:

- Any sign, symptom, or physical examination finding that worsens in nature, severity, or frequency compared to baseline irrespective of association with the condition under study
- Any clinically significant laboratory abnormality or laboratory abnormality that requires medication or hospitalization
- Reactions to IMP including those occurring as a result of an overdose, abuse, withdrawal
 phenomena, sensitivity, or toxicity
- Concurrent illness
- Injury or accident.

Conditions present prior to enrollment are considered Medical History. Pre-existing conditions should be reported as a TEAE if there is a change in the frequency, intensity, or the character of the condition.

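### The partial-date rule in Section 9.2.3 sends an event recorded under a pre-dose onset to medical history even if it worsened on treatment, although Sections 9.2 and 12.1.2 count it as a TEAE

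*Combined protocol and SAP*

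**What the plan says.** Section 9.2.3 starts from a cautious default: "Adverse events with missing or partial onset date will be treated as TEAEs". It then makes an exception, "unless the partial onset date or end date of the event is complete enough to indicate that the event started or resolved prior to" (that is, dosing on Day 1), and gives the consequence: "in which case it will be documented in medical history".

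The definition of a TEAE in Section 9.2 has two limbs. The first is onset after dosing: "Treatment-emergent AEs (hereafter referred to as AEs) are defined as those with onset after the first dose of randomized treatment intervention at Day 1". The second covers an event that, "if occurring prior to administration of the first dose at Day 1, worsened after administration of that first dose". Section 12.1.2 agrees with the second limb: "Pre-existing conditions should be reported as a TEAE if there is a change in the frequency, intensity, or the character of the condition".

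Two other places matter. For the screening period, Table 7 in Section 8.4.1 instructs sites: "Report as AE/SAE only if related to trial-specified procedure (medical history otherwise". Section 3 lists "Incidence and severity of AEs" first among the primary endpoints, and Section 9.2 uses the short form AE to mean TEAE from its definition onward.

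**The concern.** The exception joins two conditions with an or. The half about resolution is sound, since an event that ended before the first dose cannot have worsened because of it. The half about starting is not, because a pre-dose start is compatible with TEAE status under the second limb of Section 9.2. Section 9.2.3 removes that limb whenever the onset date is partial but clearly pre-dose.

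Whether an event is counted then depends on how completely its onset date was written down, which has no clinical meaning. An event lost this way leaves the incidence table and also the severity and relationship tables, since all are built on TEAEs. The clause also runs against the rest of Section 9.2.3, which resolves doubt conservatively: missing dates default to TEAE, missing grade to severe and missing relationship to related.

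**Working it through.** The plan gives no figure on this point to reproduce. The check is to apply both rules to every combination of onset, resolution and worsening for an event with a missing or partial onset date.

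Inputs: the two-limb definition in Section 9.2, and the default and exception in Section 9.2.3.

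| What the available dates show | Worsened after first dose? | Section 9.2 | Section 9.2.3 |
|---|---|---|---|
| Started pre-dose, resolved pre-dose | no | not a TEAE | medical history |
| Started pre-dose, ongoing | no | not a TEAE | medical history |
| **Started pre-dose, ongoing** | **yes** | **TEAE** | **medical history** |
| Started post-dose | either | TEAE | TEAE |
| Start unknown, not shown to have resolved pre-dose | yes | TEAE (by either limb) | TEAE |
| Start unknown, not shown to have resolved pre-dose | no | cannot be decided | TEAE (conservative default) |
| Start unknown, end date shows pre-dose resolution | no | not a TEAE | medical history |

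The rules give opposite answers in exactly one row, the third.

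Now hold the event fixed (began before Day 1, still present, worse on treatment, kept as one record under its original onset) and vary only the onset date:

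1. Full pre-dose date: Section 9.2.3 does not apply, and Section 9.2 makes it a TEAE.
2. Year or month only, clearly pre-dose: medical history under Section 9.2.3.
3. Date wholly missing: TEAE by the default in Section 9.2.3.

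More information and less information both lead to the event being counted. Only the middle case loses it. That cannot be the intention.

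The SAP deferral does not help. Section 9.2.3 leaves to the SAP only the imputation of missing or partial dates. Imputation cannot change the answer for an event whose partial date already proves a pre-dose start. No SAP text in the documents restores the worsening limb.

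There is a separate mismatch with Table 7, which keeps procedure-related screening events as AEs. Read literally, Section 9.2.3 would relabel such an event as medical history if its onset date is partial and clearly pre-dose. If the event did not worsen after dosing, this is a labelling matter only and no TEAE is lost.

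**The case against.** The strongest reply is that the recording rules mostly prevent the case. Section 12.1.2 puts conditions present before enrollment in medical history and asks for a changed one to be reported as a TEAE. Section 12.2.3 describes what goes on the AE form so as to include a worsening in severity or frequency of a pre-existing condition, with onset after consent. On that reading, a long-standing complaint that worsens at Week 4 yields a medical history entry plus a new AE dated around Week 4, and Section 9.2.3 does not touch the new AE. Events are also asked about at every visit, and a care partner is required, so partial dates for on-study events should be uncommon. This stands, and it is why the effect is probably small. It does not remove the conflict: the second limb of Section 9.2 still provides for events whose occurrence predates dosing, and Section 9.2.3 defeats it for those with a partial, clearly pre-dose date.

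A second reply is that Section 9.2.3 only settles when an event began, and Section 9.2 then decides its status. The text goes further than that: it names a destination, medical history, and a programmer would apply it as written.

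A reader might infer more than the documents support, in four ways.

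- That every AE with a pre-dose start is affected. Fully dated events fall under Section 9.2 alone.
- That a count per arm can be given. The documents contain no rate for worsening of pre-dose conditions, for partial dates or for how sites log worsening, so any count would rest on invented inputs.
- That the rule strips out any drug-related excess and so biases the comparison toward safety. It reaches one narrow type of record. Laboratory, vital sign and ECG summaries do not depend on AE onset dates, and safety p-values are nominal and descriptive (Section 9.2.2).
- That a headache after the baseline lumbar puncture, with month-only pre-dose onset and no later worsening, is a lost TEAE. Neither section counts it as one.

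**Conclusion.** The point holds as a contradiction in the text. For an AE recorded under its original onset, with a partial date that still shows a pre-dose start and with worsening after first dose, Section 9.2.3 says medical history while Sections 9.2 and 12.1.2 say TEAE.

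Its size cannot be computed from the documents. It is probably small, and it is zero if every worsening is logged as a separate AE with its own onset date. The direction is known: any error undercounts TEAEs in the primary endpoint. Whether it would fall unequally on the arms is not known.

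The conclusion rests on reading Section 9.2.3 as written and on at least some records keeping the original onset. It is worth correcting because TEAE status should not depend on whether the day of onset was recorded, and because the correction is easy before database lock.

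**What to change.** Reword the exception in Section 9.2.3, and carry it into the SAP, along these lines:

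*An event with a missing or partial onset date is treated as a TEAE unless (a) the available dates show that it resolved before first dose, or (b) the partial onset date shows that it started before first dose and the recorded data show no worsening after first dose, per the TEAE definition in Section 9.2. Events excluded in this way are non-treatment-emergent. Procedure-related screening events remain AEs per Table 7.*

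Condition (b) relies on recorded data and not on the date, because a date cannot show whether an event worsened. If the record does not settle the question, the event stays a TEAE, in keeping with the rest of the section. With this wording, the third row of the table becomes a TEAE under both sections and no other row changes its TEAE status.

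The cost is one amended sentence and its consequences in Section 9.2.3, matched in the SAP. The only downside is a slightly higher TEAE count.
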